10. STUDY ENDPOINTS

10.1. Primary Endpoint

The primary endpoint is ORR using iRECIST, which is defined as the proportion of subjects with PR or CR according to iRECIST. Subjects who discontinue due to toxicity or clinical progression prior to post-baseline tumor assessments will be considered as non-responders. Subjects who discontinue for reasons other than toxicity or clinical progression prior to the post-baseline tumor assessments or for other reasons prior to their first dose of study drug will be replaced and not included in the primary efficacy analysis.

10.2. Secondary Endpoints

The secondary endpoints are as follows:

- ORR by RECIST v.1.1.
- Safety assessed by the following measures:
 - Number of patients who have grade 3 or above drug-related toxicities
 - Frequency of drug-related toxicity by grade
 - Plerixafor- and cemiplimab-related infusion reactions
 - Immune-related AEs
 - Unacceptable toxicities
 - Vital signs: BP, pulse, respiratory rate, temperature
 - Physical examination
 - Changes in ECG readings
 - Clinical hematology: complete blood count (CBC) with differential ANC, ALC, AEC, and platelet count
 - Clinical serum chemistry: sodium, potassium, chloride, bicarbonate, glucose, BUN, creatinine, ALT, AST, alkaline phosphatase, total bilirubin, direct bilirubin, amylase, lipase, total protein, albumin, calcium, magnesium, and phosphorus
 - TSH, T3, Free T4

10.3. Exploratory Endpoints

The exploratory endpoints are as follows:

- Overall survival (OS), progression free survival (PFS), time to-progression (TTP), disease control rate (DCR), best overall response (BOR), duration of response (DOR), duration of clinical benefit (DCB), and time to objective response (TTOR) measured by iRECIST and RECIST 1.1 (**Appendix B**).
 - Overall survival (OS) is defined as the number of months from the date of first treatment until death or end of follow-up (OS will be censored on the date the subject was last known to be alive for subjects without documentation of death at the time of analysis).
 - Progression-free survival (PFS) is defined as the number of months from the date of first treatment to disease progression (PD or relapse from CR as assessed using

RECIST 1.1 criteria) or death due to any cause. PFS will be censored at the date of the last scan for subjects without documentation of disease progression at the time of analysis. iPFS is defined as the time to iUPD if the next scan (4-8 weeks later) confirms PD (state change from iUPD to iCPD, time to progression defined in this instance as iUPD).

- Disease Control Rate (DCR) is defined as the percentage of subjects achieving stable disease or better (SD + PR + CR).
- Best Overall Response (BOR) is defined in **Appendix B**.
- Duration of Response (DOR) is defined as the number of months from the first documentation of a response to date of disease progression.
- Duration of Clinical Benefit (DCB) is defined as the number of months from the date of first treatment to date of disease progression in those achieving a PR or CR.
- Time to Objective Response (TTOR) is defined as the number of months from the date of first treatment to the date of documented partial or complete response.
- Time to-progression (TTP) is defined as the number of months from the date of first treatment to the date of documented disease progression (PD or relapse from CR as assessed using RECIST 1.1 criteria). It differs from PFS in that it does not include death in the definition of an event. TTP will be censored at the date of the last scan for subjects without documentation of disease progression at the time of analysis.
- Immune subset analysis by IHC and gene expression profiling of the tumor
- Sequencing of tumor
- Immune subset analyses in PBMCs including effector, helper, and regulatory T cells, NK cells and macrophages
- T cell receptor (TCR) repertoire analysis in PBMCs and tumors
- Gene expression analysis
- cfDNA analysis
- Steady-state plerixafor concentrations to correlate with pharmacodynamic endpoints (e.g., safety, response, and correlative studies).

11. DATA REPORTING/ REGULATORY REQUIREMENTS

AE guidelines and instructions for AE reporting can be found in **Section 6 (Adverse Events: List and Reporting Requirements)**.

Each Principal Investigator will comply with all regulated local reporting requirements and regulations, including ICH E6 guidelines for Good Clinical Practices.

11.1. Data Collection and Processing

All information will be collected on study-specific CRFs by study staff. These data will be reviewed for completeness and accuracy by the Principal Investigator.

CRFs will be used to capture study results and data. The study coordinator or other authorized study personnel will transcribe data from source documents onto eCRFs. Before or between visits, the Protocol Chair, or designee may request copies of the CRFs for preliminary medical review.

Once the CRFs are complete and source-verified, the investigator must sign and date all required pages, verifying the accuracy of all data contained within the CRF.

11.2. Safety Meetings

Scheduled meetings will take place weekly (or as needed based on enrollment) and will include the protocol principal investigator, study coordinator(s), research nurse(s), sub-investigators (as appropriate), collaborators (as appropriate), and biostatisticians (as appropriate) involved with the conduct of the protocol. During these meetings, matters related to the following will be discussed: safety of protocol participants, validity and integrity of the data, enrollment rate relative to expectation, characteristics of participants, retention of participants, adherence to protocol (potential or real protocol violations), data completeness, and progress of data for objectives.

11.3. Monitoring

The SKCCC Compliance Monitoring Program will provide external monitoring for JHU-affiliated sites in accordance with SKCCC DSMP (Version 6.0, 02/21/2019). The SMC Subcommittee will determine the level of patient safety risk and level/frequency of monitoring. The PI shall internally monitor the progress of the trial, including review and confirmation of all safety/treatment-related outcomes, response assessments, safety reports and/or any related source documentation. The protocol will be monitored externally by the SKCCC CRO QA Office. Additional data and safety monitoring oversight will also be performed by the SKCCC Safety Monitoring Committee (SMC - as defined in the DSMP).

11.4. Study Documentation

11.4.1. Informed Consent and Authorization for use and Disclosure of Protected Health Information

Written informed consent and authorization of use and disclosure of protected health information (PHI) must be obtained from each subject (or the subject's legally authorized representative) before performing any study-specific screening/baseline period evaluations. The ICF and authorization for use and disclosure of PHI, which is prepared by the investigator or the site, must be reviewed and approved by the Protocol Chair (or designee), the study monitor (if applicable), and the site's IRB before the initiation of the study.

11.4.2. Investigator Study Files

Documentation about the investigator and study staff, the IRB and the institution, is required before study site initiation. A list of required documents will be provided by the Protocol Chair designee to each participating investigator. Copies of these documents as well as supplemental information, such as the investigator's obligations, IB, clinical study protocol and amendments, safety information, investigational agent information, biological samples and laboratory procedures, SRM, study logs, and Protocol

Chair/investigator/study monitor correspondence will be kept on-site in study site-specific files.

The Protocol Chair or designee will be responsible for maintaining original and backup of all CRF data. The investigator is responsible for maintaining backup of all electronic data systems used for primary documentation or source documentation. Backup of electronic data will be performed periodically as described in the site-specific SOPs. Backup records must be stored at a secure location on site and backup and recovery logs must be maintained to facilitate data recovery. If an electronic medical records system that is not supported by the Protocol Chair or designee (or is discontinued or decommissioned) is used, the investigator must maintain a system to retrieve these records or arrange for the transfer of these records to an alternate electronic format or to paper.

Changes to any electronic records require an audit trail, in accordance with 21 CFR 11.10(e), and should include who made the changes and when and why the changes were made. An audit trail is defined as a secure, computer-generated, time-stamped electronic record that will allow reconstruction of the course of events relating to the creation, modification and deletion of an electronic record. Audit trails must be created incrementally, in chronological order and in a manner that does not allow new audit trail information to overwrite existing data. Audit trails should be in a readable format and readily available at the study site and any other location where electronic study records are maintained.

Audit trails are generated automatically for eCRFs. The investigator is responsible for maintaining audit trails of all electronic data systems used for primary documentation or source documentation.

11.4.3. Case Report Forms and Source Documentation

The investigator must make study data accessible to the site monitor, to other authorized representatives of the Protocol Chair (or designee) and to the appropriate regulatory authority inspectors. The original CRF for each subject will be checked against source documents at the study site by the site monitor.

11.4.4. Retention of Study Documents

According to ICH E6, all CRFs, as well as supporting paper and electronic documentation and administrative records, must be retained for at least 2 years after the last approval of a marketing application and until there are no pending or contemplated marketing applications, or at least 2 years have elapsed since the formal discontinuation of clinical development of an individual product. Longer retention periods may apply. The Protocol Chair (or designee) will notify investigators as to when documents no longer need to be retained. No study documents will be destroyed or moved to a new location without prior written approval from the Protocol Chair (or designee). If the investigator relocates, retires or withdraws from the clinical study for any reason, all records required to be maintained

for the study should be transferred to an agreed-upon designee, such as another investigator at the institution where the study was conducted.

Audit trails for electronic documents must be retained for a period at least as long as that required for the subject electronic records to which they pertain. The investigator must retain either the original or a certified copy of audit trails.

11.4.5. Data Confidentiality and Subject Anonymity

All information about the nature of the proposed investigation provided by the Protocol Chair or their representative to the investigator (with the exception of information required by law or regulations to be disclosed to the IRB, the subject or the appropriate regulatory authority) must be kept in confidence by the investigator.

The anonymity of participating subjects must be maintained. Subjects will be identified by their initials and an assigned subject number on CRFs and other documents retrieved from the site or sent to the Protocol Chair, study monitor, Sanofi, regulatory agencies, or central laboratories/reviewers. Documents that identify the subject (e.g., the signed ICF) must be maintained in strict confidence by the investigator, except to the extent necessary to allow auditing by the appropriate regulatory authority, the study monitor, Protocol Chair or their representative.

12. STATISTICAL CONSIDERATIONS

12.1. Study Design/Endpoints

Sample Size

This is an open-label, two stage, phase 2 study to evaluate the safety and clinical activity of plerixafor and cemiplimab in patients with metastatic pancreatic adenocarcinoma. The primary endpoint is objective response rate (ORR) assessed using iRECIST.

The treatment regimen would be considered of insufficient activity for further study in this population if response rate (irORR) is 7.7% or less[1], and the minimum required level of efficacy that would warrant further study is an irORR of 20%. The sample size is calculated to detect an improved irORR from 7.7% to 20%. A modified Simon's two-stage design is planned. A total of 21 patients will be entered in the first stage. If ≤ 1 subject responds, the treatment will be terminated and we will conclude the regimen is ineffective. If ≥ 2 subjects respond, then additional 18 patients will be enrolled. If a total of 5 or fewer subjects respond in stage one and two combined, we consider the regimen ineffective. If a total of 6 or more respond, we conclude the regimen is promising and warrant further study. The maximum sample size will be 39.

The design provides 80% power to detect the difference between the null hypothesis irORR of 7.7%[1] to the alternative rate of 20% with one-sided type I error 0.07 (target type I error 0.1). The probability of early stopping at first stage is 0.51 if the true irORR is 7.7%.

Statistical Analyses

The primary endpoint is objective response, defined as complete response (CR) or partial response (PR) per iRECIST. Objective response rate (irORR) will be estimated as the proportion of subjects whose best overall response is either a CR or PR with corresponding 95% CI. The evaluable population for the analysis is all subjects who receive at least one dose of study drug, and have at least one post-baseline tumor assessments or discontinue due to toxicity or clinical progression prior to post-baseline tumor assessments.

Exploratory endpoints include progression-free survival (PFS), overall survival (OS), and objective response per RECIST 1.1, duration of response (DOR), disease control (DCR), time to progression (TTP). PFS is defined as the time from the first day of study treatment to the date of the first documented tumor progression or death due to any cause, whichever occurs first. Subjects who did not progress or die will be censored on the date of their last tumor assessment. Overall survival (OS) is the time from the first day of study treatment to the date of death due to any cause. A subject who has not died will be censored at last known date alive. Kaplan-Meier curves will be used to summarize OS. Time to-progression (TTP) is defined as the number of months from the date of first treatment to the date of documented disease progression (PD or relapse from CR). Among patients with an objective response, DOR is defined as the time between the date of initial complete or partial response to the date of the first documented tumor progression or death due to any cause. Subjects who neither progress nor die will be censored on the date of their last tumor assessment. Summary statistics will be presented for DOR. Kaplan-Meier method will be used to summarize time-to-event outcomes PFS, OS, TTP and DOR. Rate of OR and DOR will be estimated along with 95% confidence intervals. The outcomes will be assessed using RECIST 1.1 and also iRECIST unless otherwise defined.

For biomarkers, potential relationships between biomarker data and efficacy or safety endpoints will be investigated aimed at identifying baseline biomarkers that may be used to prospectively identify subjects likely (or not likely) to respond to the treatment and to identify subjects who may be predisposed to having adverse reactions to treatment. Steady-state plerixafor concentrations will be correlative with response using appropriate non-parametric analysis. These exploratory biomarker analyses will be completed with biomarkers measured in blood and in tumor samples.

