1. OBJECTIVES

1.1. Primary Objective

To estimate the objective response rate (ORR) using immune RECIST (iRECIST) in patients with metastatic pancreatic cancer treated with plerixafor and cemiplimab.

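### Does the primary irORR estimate in Section 12.1 need a named confidence interval method and an adjustment for the stage 1 futility stop?

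*Combined protocol and SAP*

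**What the plan says.** The primary objective in Section 1.1 is "To estimate the objective response rate (ORR) using immune RECIST (iRECIST) in patients with metastatic pancreatic cancer". Section 12.1 (Statistical Analyses) gives the estimator and interval: irORR is "estimated as the proportion of subjects whose best overall response is either a CR or PR with corresponding 95% CI". Later in the same section, "Rate of OR and DOR will be estimated along with 95% confidence intervals". Neither sentence names a method.

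The decision rule is in the Sample Size part of Section 12.1. The regimen is of "insufficient activity for further study in this population if response rate (irORR) is 7.7% or less", and "the minimum required level of efficacy that would warrant further study is an irORR of 20"%. "A total of 21 patients will be entered in the first stage"; the trial ends there if 1 or none responds, and otherwise enrols 18 more. "If a total of 6 or more respond, we conclude the regimen is promising and warrant further study". The stated operating characteristics are 80% power, "one-sided type I error 0.07 (target type I error 0.1"), and a 0.51 probability of stopping early at a true 7.7%. The rule uses counts alone; nothing ties it to the interval.

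**The concern.** Three things look wrong.

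- **The estimator.** A trial that stops after a poor first stage keeps its low proportion, while one that starts well is diluted by further data. Averaged over all possible trials, the raw proportion is therefore biased downward.
- **The interval.** Wald, Wilson and exact limits all fit the words of the plan. They differ in limits and, more importantly, in coverage, and the choice could be made after the data are seen.
- **The link to the decision.** The rule runs at a one-sided error of 0.07, whereas a two-sided 95% interval spends 0.025 per tail. A trial could be declared promising while its interval contains the null rate.

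At stake is the main reported number of a trial set up to estimate a response rate.

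**Working it through.** **Inputs (Section 12.1).** p0 = 0.077; p1 = 0.20; n1 = 21, stop if X1 ≤ 1; n2 = 18; N = 39; success if total S ≥ 6.

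**1. The plan's own figures.**
- Early stop at 7.7%: 0.923^21 + 21 × 0.077 × 0.923^20 = 0.186 + 0.326 = 0.51.
- P(success) = Σ over x = 2 to 21 of P(X1 = x) × P(X2 ≥ 6 − x). This is 0.0725 at 7.7% and 0.805 at 20%.

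All three agree with the plan at its stated precision.

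**2. Bias of the raw proportion.** Mean = P(stop) × mean given stop + P(continue) × mean given continue.
- True 7.7%: 0.5115 × 3.03% + 0.4885 × 10.33% = 6.60%, a bias of −1.1 points.
- True 20%: 0.0576 × 4.00% + 0.9424 × 20.53% = 19.57%, a bias of −0.4 points.
- Bias is −1.1 points at 10% and −0.8 at 15%.

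The downward direction holds only on average over all trials. Among trials that reach stage 2, the raw proportion is high: 10.3% when the truth is 7.7%.

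**3. Effect of adjusting for the stages.** The comparator is the uniformly minimum variance unbiased estimator (UMVUE), Σ C(20, x−1)C(18, s−x) / Σ C(21, x)C(18, s−x) for x = 2 to s. It is paired with the exact two-stage interval under stage-wise ordering.

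| Result | Raw | Clopper-Pearson 95% | UMVUE | Two-stage exact 95% |
|---|---|---|---|---|
| 2/39 | 5.1% | 0.6–17.3% | 9.5% | 1.2–23.9% |
| 3/39 | 7.7% | 1.6–20.9% | 10.8% | 2.0–24.5% |
| 5/39 | 12.8% | 4.3–27.4% | 14.1% | 4.4–28.2% |
| 6/39 | 15.4% | 5.9–30.5% | 16.1% | 5.9–30.8% |

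If the trial stops at 0/21 or 1/21 the two intervals coincide, because the stage-wise ordering is then just the order of X1. The visible differences are at 2 to 5 of 39, where the rule has already declared the regimen ineffective. Those counts have probability 41.6% at a true 7.7% and 13.7% at 20%.

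**4. Coverage of a nominal 95% interval under this design.**

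| Method | True 7.7% | True 20% | Lowest, 3–35% |
|---|---|---|---|
| Clopper-Pearson, stages ignored | 99.1% | 97.3% | 94.6% |
| Two-stage exact | 99.1% | 97.5% | 95.5% |
| Wilson | 97.3% | 95.3% | 91.9% |
| Wald | 80.5% | 87.1% | – |

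Clopper-Pearson is below 95% on about 5% of a 0.1-point grid, by at most 0.5 point. Wald's shortfall comes mainly from the method: in a single-stage trial of 39 it covers 80.4% and 89.8%.

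**5. Is the unbiased estimator better?** Root mean squared error in percentage points, UMVUE against raw: 5.4 against 4.9 at 7.7%; 5.8 against 5.7 at 10%; 6.4 against 6.7 at 15%; 6.8 against 7.1 at 20%. At a true 7.7%, among trials reaching stage 2, the UMVUE averages 12.6% against 10.3% raw; among trials declared promising, 17.3% against 16.8%. At 2/39 it equals 20/210 = 2/21, so the 18 stage 2 patients without a response carry no weight.

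**6. Interval against decision.** The stage-wise one-sided p-value against 7.7% is 0.0725 at 6/39 and 0.0271 at 7/39. Both exceed 0.025, so the two-stage exact interval contains 7.7% at both counts. This follows from comparing a 0.07 rule with 0.025 per tail.

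**The case for a change.** The best case for a change is that the plan permits a poor interval and one line would rule it out. At 6/39, Wald gives 4.1–26.7%, Wilson 7.2–29.7% and Clopper-Pearson 5.9–30.5%. Wald has zero width at 0/21, an outcome with probability 18.6% at a true 7.7%. At 7/39, Wilson excludes 7.7% (lower limit 9.0%), while Wald (5.9%), Clopper-Pearson (7.5%) and the two-stage interval (7.6%) do not, so a choice made after the data could colour the report. At 2/39 the unadjusted exact interval excludes the 20% target and the adjusted one does not. At a true 20%, 15% of successful trials finish at exactly 6/39, where all four intervals contain 7.7% and a reader may see a contradiction.

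The arithmetic stands; the need for a change does not follow. The plan never mentions Wald, and an exact interval is the ordinary choice at these sample sizes. The 2/39 result has probability 0.2% when the truth is 20%. Section 12.1 already bases the decision on the count, so a sentence saying so would repeat it, and the plan calls for no p-value for irORR.

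A compulsory two-stage interval also has a practical weakness. Section 12.2 adds toxicity monitoring that halts enrolment, with a stated 45.8% chance of stopping at a 20% event risk. If such a halt became permanent, the final number need not be 21 or 39, and the two-stage interval and the UMVUE would not apply as defined. Clopper-Pearson works at any number.

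**Conclusion.** No change follows. The missing method name is a detail that analysts fill sensibly, and the choice between raw and adjusted estimates is a fair trade-off. With an ordinary exact interval, the plan gives a point estimate whose average bias is about −1.1 points at 7.7% and 10% and smaller at 15% and 20%. Interval coverage is 94.6% or more for true rates of 3% to 35%, and at 6/39 the limits differ from the adjusted ones by 0.3 point at most. Type I error, power and early-stopping probability are untouched.

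This rests on three assumptions: the analyst uses an exact interval (Wilson would dip to 91.9%, and Wald would be materially worse); responses are independent with a common probability; and the trial ends at 21 or 39 evaluable patients. A report can usefully call the estimate unadjusted for the interim look, but the plan need not be amended for that.

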12.2. Safety Analysis

The safety analysis will be performed in all treated subjects. AE data will be listed individually and incidence of AEs summarized by system organ class and preferred terms within a system organ class for each cohort. When calculating the incidence of AEs, each AE (based on preferred terminology defined by CTCAE version 5.0) will be counted only once for a given subject. In analyses of grade and causality, if the same AE occurs on multiple occasions, the highest grade and strongest relationship to study drug will be assumed. If 2 or more AEs are reported as a unit, the individual terms will be reported as separate experiences.

Changes in vital signs, hematology and clinical chemistry parameters from baseline to the end of the study will be examined. Toxicity will be tabulated by type and grade. Toxicities will be

characterized according to the CTCAE version 5.0. Treatment-emergent changes from normal to abnormal values in key laboratory parameters will be identified.

The study will include a safety run-in for the first six patients. If more than 1 of the first 6 patients experiences an unacceptable toxicity within the first cycle, then enrollment will be halted and the overall risk-benefit ratio of the study will be reconsidered. At any time thereafter, if more than 33% of patients are observed to experience unacceptable toxicity within the first cycle, enrollment will be halted and the safety of the combination will be re-evaluated. Complete unacceptable toxicity criteria can be found in **Section 4.7**. The enrollment stops if:

Number of Patients with AE > 33%	2	3	4	5	6	7	8	9	10	11	12	13
In number of patients between	6	7-9	10-12	13-15	16-18	19-21	22-24	25-27	28-30	31-33	34-36	37-39

The operating characteristics of this stopping rule for toxicity, starting from the 6th patient, are shown below and based on 5000 simulations.

Risk of AE	0.10	0.20	0.25	0.30	0.33	0.40	0.45	0.50	0.55	0.60
% of time study stops	12.4%	45.8%	63%	78.7%	85%	96.3%	99%	99.7%	100%	100%
Expected sample size	34.98	24.64	19.62	15.25	13.02	9.04	7.69	6.81	6.41	6.19

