6.2. Relationship

The relationship of an AE to the administration of the study drug is to be assessed by the investigator according to the following definitions:

- No (unrelated, not related, no relation): The time course between the administration of study drug and the occurrence or worsening of the adverse event rules out a causal relationship and another cause (concomitant drugs, therapies, complications, etc.) is suspected.
- Yes (related): The time course between the administration of study drug and the occurrence or worsening of the adverse event is consistent with a causal relationship and no other cause (concomitant drugs, therapies, complications, etc.) can be identified.

The following factors should also be considered:

- The temporal sequence from study drug administration - The event should occur after the study drug is given. The length of time from study drug exposure to event should be evaluated in the clinical context of the event.
- Underlying, concomitant, intercurrent diseases - Each report should be evaluated in the context of the natural history and course of the disease being treated and any other disease the subject may have.
- Concomitant medication - The other medications the subject is taking or the treatment the subject receives should be examined to determine whether any of them might be recognized to cause the event in question.
- Known response pattern for this class of study drug - Clinical and/or preclinical data may indicate whether a particular response is likely to be a class effect.

- Exposure to physical and/or mental stresses - The exposure to stress might induce adverse changes in the recipient and provide a logical and better explanation for the event.
- The pharmacology and pharmacokinetics of the study drug - The known pharmacologic properties (absorption, distribution, metabolism, and excretion) of the study drug should be considered.

Assessment of Grade:

The investigator will make an assessment of grade for each AE and SAE reported during the study, which will be recorded in the CRF. The assessment will be based on the National Cancer Institute's CTCAE (Version 5.0) and graded as shown below:

- Grade 1: Mild; asymptomatic or mild symptoms; clinical or diagnostic observations only; intervention not indicated
- Grade 2: Moderate; minimal, local or noninvasive intervention indicated; limiting age-appropriate instrumental activities of daily living

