- Grade 3: Severe or medically significant but not immediately life-threatening; hospitalization or prolongation of hospitalization indicated; disabling; limiting self-care activities of daily living
- Grade 4: Life-threatening consequences; urgent intervention indicated
- Grade 5: Death related to AE

Any AE that changes in grade during its course will be recorded in the CRF at the highest level experienced by the subject.

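### Section 12.2 takes the highest grade and the strongest relationship of a repeated AE separately, so the grade-by-relationship endpoints in Section 10.2 can count a grade 3+ drug-related toxicity that no episode was

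*Combined protocol and SAP*

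**What the plan says.** Section 12.2 (Safety Analysis) reduces the AE data to one record per preferred term per subject: each AE "will be counted only once for a given subject". It then says how that record is filled. "In analyses of grade and causality", the rule is that "if the same AE occurs on multiple occasions, the highest grade and strongest relationship to study drug will be assumed". Nothing is said about grade and relationship having to come from the same occurrence.

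The first two safety measures in Section 10.2 combine the two attributes: "Number of patients who have grade 3 or above drug-related toxicities" and "Frequency of drug-related toxicity by grade". Neither section gives these measures a derivation of their own.

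Section 6.2 sets up the relationship scale: "The relationship of an AE to the administration of the study drug is to be assessed by the investigator according to the following definitions". There are two categories, unrelated and related, so the strongest relationship is simply related if any occurrence was related. The same section fixes the grade within a single event: "Any AE that changes in grade during its course will be recorded in the CRF at the highest level experienced by the subject". Section 12.2 also states that "AE data will be listed individually", so the occurrence-level data will exist.

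**The concern.** Taking a maximum over grade and a separate maximum over relationship is sound when each is reported alone. It fails when they are reported jointly, because the two maxima can come from different episodes. The collapsed record then describes an event that no investigator recorded.

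Both affected measures serve the secondary objective of characterizing the toxicity of the combination (Section 1.2.2). The trial has a single arm, so no comparison group would reveal an excess. Repeats with different causes are plausible here: related and unrelated AEs are both collected (Section 6.5.1), treatment may last up to two years (Section 4.9), and it may continue beyond RECIST 1.1 progression (Section 4.10.1).

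**Working it through.** The plan states no figure for this point, so there is none to reproduce. The check is one of logic, followed by a range under a stated assumption.

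**1. One subject, one preferred term, two separate occurrences**

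| | Grade | Relationship |
|---|---|---|
| Occurrence A | 1 | related |
| Occurrence B | 3 | unrelated |
| Record under Section 12.2 | max(1, 3) = 3 | related, because A is related |

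- Rule as written: grade 3 or above and related, so the subject counts.
- By occurrence: A is related but grade 1; B is grade 3 but unrelated. Neither is both, so the subject should not count. The related toxicity is grade 1.

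**2. Direction**

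If any single occurrence is both grade 3+ and related, the highest grade is at least 3 and the strongest relationship is related, so the rule also counts that subject. The rule therefore never misses a true case and can only add false ones. In the table of drug-related toxicity by grade, the number of subjects with a related term is unchanged, but a discordant subject moves to a higher grade row, since the highest grade over all occurrences is at least the highest grade over the related ones.

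**3. Size for the patient count of grade 3+ drug-related toxicity**

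Inputs: a maximum of 39 subjects (Section 12.1), and q, the proportion of treated subjects whose only claim to a grade 3+ related toxicity is a discordant pair. The documents do not give q; the values below are assumptions. Expected miscounts are 39 × q. The chance of at least one is 1 − (1 − q)^39, taking subjects as independent.

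| q (assumed) | 39 × q | 1 − (1 − q)^39 |
|---|---|---|
| 1% | 0.4 | 0.324 |
| 2% | 0.8 | 0.545 |
| 5% | 2.0 | 0.865 |
| 10% | 3.9 | 0.984 |

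**4. What one miscounted subject does to the rate**

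With exactly 39 treated subjects, one miscount moves the rate by 1/39 = 2.6 percentage points. This holds only for a subject with no genuine grade 3+ related event of any term; otherwise that subject is already in the count and adds nothing. The denominator is all treated subjects (Section 12.2). It may exceed 39, because Section 10.1 replaces some subjects who discontinue before a post-baseline scan, and it would be about 21 if the trial stopped after stage one.

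**5. What the rule does not reach**

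The run-in and 33% rules in Section 12.2 use unacceptable toxicity, which Section 4.7 defines through the discontinuation criteria of Section 4.10.2 and not through the collapsed AE record. The primary endpoint is response by iRECIST.

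**The case against.** **The sentence may mean two separate summaries.** It can be read as one table by grade and one by causality, and then each maximum is right. The plan does not say so, and the two Section 10.2 measures would still have no rule for pairing grade with relationship. The gap remains on either reading.

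**The documents narrow the cases.** Expected progression of the disease is not recorded as an AE (Section 6.1.1), which removes some severe late unrelated episodes. Continuous worsening is one event recorded at its highest grade (Section 6.2), so only separate occasions matter. An unrelated judgement requires the time course to rule out a causal link. These points stand and argue for a small number. They do not bring it to zero: a related judgement in turn requires that no other cause can be identified, so a severe repeat from infection, a procedure or another drug may still be recorded as unrelated.

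**The direction is cautious and the listings allow correction.** True: the rule can overstate drug-related severity but not hide it, and a reader of the listings could recover the pairing. That limits the harm. The summary endpoint would still be wrong for the patients concerned.

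**A stronger reading is tempting.** A reader might treat repeat episodes as independent and infer a large, predictable bias. With two occurrences, probability r of related and g of grade 3+, the true rate is 1 − (1 − rg)² and the rule gives [1 − (1 − r)²][1 − (1 − g)²]. At r = 0.5 and g = 0.2 these are 19.0% and 27.0%. Over r from 0.3 to 0.7 and g from 0.1 to 0.2, the relative excess runs from 26% (0.260 against 0.328) to 64% (0.059 against 0.097), or about 1.5 to 3.1 of 39 subjects if every subject has such a term. The documents do not support this. They give neither r nor g, nor the frequency of repeats, and they give no ground for independence. The investigator weighs the same causality factors each time (Section 6.2), so agreement between episodes is likely; with full agreement the excess is zero.

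**Conclusion.** The point holds as a defect in a stated derivation rule. Followed literally, Section 12.2 can report a grade 3+ drug-related toxicity that no occurrence was, and the plan offers no other derivation for the two endpoints concerned. The direction is certain: upwards only. The size is not known. Under the assumption that 1% to 10% of 39 treated subjects have only a discordant pair, between 0.4 and 3.9 would be miscounted; if relationship agrees across repeats, none would be.

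The consequence is confined to descriptive secondary safety results. A reader might also infer that the toxicity stopping boundary is triggered too readily. It is not affected, since it counts unacceptable toxicities in the first cycle under Sections 4.7 and 4.10.2. The efficacy decision is likewise unaffected.

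**What to change.** Add one sentence to Section 12.2: *For summaries that combine grade and relationship, the highest grade among the occurrences assessed as related is used.* Keep the highest grade over all occurrences for the all-cause table, and the strongest relationship for a table by relationship alone.

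The cost is one programming step: restrict to related occurrences before taking the maximum grade. The individual AE records already planned are sufficient, so no new data are needed. The downside is that the grade 3+ drug-related count becomes slightly less conservative, because it then rests on the investigator's relationship judgement for each occurrence. The all-cause table by highest grade keeps every severe episode visible.
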